**Effect of Hindmilk on Growth Velocity of Very Preterm Infants
(REB-18-0195)**

Primary Investigator: [name] MSc

Co-Investigators:

[name], Neonatal-Perinatal Fellow
[name] LC (recruitment)
[name]
[name] FAAP
[name], Neonatal-Perinatal Fellow
[name], RD

Project Summary:

Extra-uterine growth restriction (EUGR) is one of the most common findings among very preterm infants at discharge from neonatal intensive care units. EUGR is associated with major morbidities such as bronchopulmonary dysplasia (BPD), retinopathy of prematurity (ROP) and impaired neurodevelopment. EUGR is caused by slow postnatal growth and largely results from energy and protein deficits. These deficits occur despite the current fortifications of human milk. Hindmilk, the milk at the end of a breast pumping session, has higher fat and energy content compared to the composite milk. Feeding hindmilk can be a natural and innovative way to provide additional calories for very preterm infant. Hindmilk is rich in some fatty acids that are currently under investigation to prevent BPD and ROP and improve neurodevelopment. The aim of this study is to assess growth benefits of feeding hindmilk and to explore whether it can improve fatty acids profile in very preterm infants.

1. What you want to do.

Hypothesis: In very preterm infants (born less than 32 weeks gestation) with poor postnatal growth velocity (<15 g/kg/day), feeding hindmilk would improve average weight gain by at least 4 g/kg per day.

Research question: Does feeding hindmilk improve weight gain in very preterm infants with poor growth velocity?

Primary outcome: Difference in average weight gain (in g/kg per day) between the week after feeding hindmilk and the week before.

Average weight gain is calculated as: (end weight – start weight in grams) / start weight then divided by number of days (7 days in our study as we use average weight gain over 7 days).

American Academy of Pediatrics continues to recommend that postnatal growth of preterm infants should approximate the intrauterine growth of fetuses of the same gestational age (15-20 g/kg per day).¹ Therefore, poor postnatal growth velocity is defined when average weight gain is less than 15 g/kg per day).

Secondary objectives/outcomes:

1. Effect of feeding hindmilk on:
 - a. Anthropometrics (weight, length and head circumference Z scores) at 36 weeks postmenstrual age (PMA) and at discharge.
 - b. Body mass index (BMI) at 36 weeks PMA and at discharge.
2. Incidence of EUGR at 36 weeks PMA and at discharge.
3. Incidence of BPD, ROP and late-onset sepsis.
4. Correlation between human milk content (fat, protein and energy) and weight gain.
5. Effect of hindmilk on erythrocyte membranes fatty acids profile.
6. Changes in mother's milk volumes after feeding hindmilk.

Note: secondary outcomes 1 to 3 will be compared between infants received hindmilk for at least 2 weeks and the rates of these outcomes among NICUs. These rates are published publically by the Canadian Neonatal Network.

2. Why this is a reasonable thing to do

The nutritional management of very preterm infants aims to result in growth patterns that approximate the intra-uterine fetal growth patterns.^{1,2} However, poor growth during NICU stay is common and results in a high rate of EUGR, one of the most common findings in very preterm infants at discharge.³⁻⁵ A study from Calgary has shown that 65% of very preterm infants are growth restricted at 37 weeks PMA.⁴ EUGR and the associated caloric and protein deficits not only cause slower growth velocity, but also are associated with major morbidities, including BPD, ROP and impaired neurodevelopment.^{2,6} Moreover, epidemiologic studies have described additional long-term health consequences of growth restriction, such as an increased risk of cardiovascular (hypertension), renal and metabolic morbidities, all explained under the concept of developmental origins of disease.⁶⁻⁸

Human milk provides the ideal nutrition for term infants. It is also recommended for preterm infants, but does not alone provide optimal nutrition. The growth and neurodevelopmental needs of very preterm infants are best met by appropriate fortification of human milk. Nonetheless, current fortification regimen (4 packets added to 100 ml of human milk) has been unsuccessful in preventing EUGR in almost two thirds of very preterm infants.⁴ Fortification with formula on top of the currently used human milk fortifiers has become a common practice to improve growth velocity. This practice increases milk osmolality which is a risk factor for feeding intolerance and necrotizing enterocolitis (NEC).⁹ Powder formulas have also been associated with increased rate of sepsis.¹⁰ Alternative sterile liquid formulations displace large amount of mother's own milk.

Foremilk and hindmilk for very preterm infants:

There is a large variation in the protein and energy contents of human milk between foremilk, the first milk that comes out of the mother's breast, and hindmilk, the milk that comes out at the end of the breast pumping session.¹¹ Foremilk is low in calories and fat compared to hindmilk. Fat content is known to be the major source for energy in the breast milk. Hindmilk is considered a natural way of providing additional calories to preterm infants. Furthermore, the degree of prematurity is inversely related to the ratio between foremilk: hindmilk volumes. This may partially explain the higher rate of postnatal growth failure in the more immature infants.¹² Although, it is difficult to precisely identify the time point in which production of hindmilk starts, current literature define hindmilk as milk collected after the first 3 minutes of pumping.^{13,14}

Nutrient composition of hindmilk in preterm infants:

In addition to the higher fat (1.2-fold) and energy (1.1-fold), concentrations of retinol α -tocopherol (vitamin A) and γ -tocopherol (vitamin E) are approximately a 1.2-fold higher in hindmilk compared to composite milk.¹³ With the higher fat concentrations, hindmilk offers a great opportunity to naturally increase intakes of long chain poly-unsaturated fatty acids (LC-PUFAs). LC-PUFAs such as docosahexaenoic acid (DHA) and arachidonic acid (AA) are considered essential for maturation of the developing brain, retina and other organs in preterm infants. Several randomized controlled trials have been recently completed to explore effects of LC-PUFAs supplementation on visual acuity, BPD and neurodevelopmental outcomes of very preterm infants.^{15,16}

Very preterm infants often have low plasma concentrations of vitamin A.¹⁷ A recent Cochrane review indicated a small reduction; although significant, in the risk of BPD with repeat intramuscular doses of vitamin A.¹⁸ The need for frequent muscular injections has limited the use of this method to prevent BPD. Vitamin E supplementation reduces risk of ROP.¹⁹ Parenteral vitamin E (intravenous and intramuscular) has been associated with increased risk on intraventricular hemorrhage (IVH) and sepsis nevertheless enteral vitamin E supplementation has been shown to be safe in 10 randomized controlled trials.¹⁹ Furthermore, the calculated daily dose that a very preterm infant will get from all enteral sources including hindmilk is significantly lower than that associated with increased risk of IVH and sepsis (30 IU/kg per day).¹⁹ Nitrogen concentrations are almost similar between hind and composite milk (1.01-fold).¹³

Availability of hindmilk in NICU:

Preterm infants require small milk volumes. Therefore, their mothers are usually able to pump more milk than infants' need. It is beneficial to the infant if the small volumes they consume are higher in fat and calories rather than watered down with the foremilk volume. On average mothers of very preterm infants produce 545 mL per 24 hours (inter-quartile range: 224, 1817).¹² Most very preterm infants on enteral feeding require less than 225 ml of human milk when their weight is less than 1500 g. Previous studies showed that 62-82% of mothers of very low birth weight (VLBW) infants produce enough milk volume to enable fractionation and hindmilk feeding after 3 weeks from delivery.^{12,20}

Use of hindmilk in Calgary:

Use of hindmilk (cream project) started in September 2016 as part of a quality improvement project to improve weight gain in very preterm infants. Eligibility criteria for including very preterm infants in the cream project are:

- 1) Infants is on full enteral feeds for more than 2 weeks
- 2) Poor weight gain (<15 g/kg per day) despite optimization of energy and protein intakes
- 3) Mothers have enough milk supply (>150% of daily needs)

Mothers are approached by NICU lactation consultants (LCs) and the benefits of higher fat milk is discussed. Mothers separate their foremilk (and freeze it to feed at a later time) from hindmilk. Mothers use the following instructions to separate their milk: "1) have extra breast milk storage containers ready, 2) begin pumping breasts with the breast pump, 3) about three minutes after the milk starts, turn the pump off. This is usually equal to one-third of the usual pumped amount, 3) label this container with "foremilk" which is frozen to be used later, 4) Change containers and continue pumping until two minutes after the milk flow stops, 5) label these bottles "hindmilk"." Hindmilk collection sheet is kept at bedside. The sheet is completed weekly by lactation consultant, participant's mother, bed side nurse and dietitian.

To date, a total of 34 mother-infant pairs were included in the cream project. Preliminary analysis for these infants revealed an increase in weight gain by 4.2 g/kg per day in the following week of using hindmilk. This analysis does not capture any change to the nutrition plan after the hindmilk use. There were 8 (23.5%) infants with limited benefit (less than 3 g/kg per day increase from the week before feeding hindmilk). Human milk analysis would

have helped identify fat and energy contents of the hindmilk of these mothers.

Hindmilk and erythrocyte membrane fatty acids profile:

The fatty acids (FAs) profile of the erythrocyte membrane measures the percentage of FAs in the red blood cells (RBCs) from a dried blood spot. Measurement of the RBC FAs provides less biological variability than the measurement in plasma because of a slower turnover rate.²¹ Dietary supplementations of LC-PUFAs for 2 weeks have been shown to significantly alter RBC FAs profile.²² Advantage of the RBC FAs profile is the small amount of blood to perform the test. FAs profile includes measurement for DHA, AA, and Eicosapentaenoic acid (EPA). Because hindmilk has 20% more fat than the composite milk, it is sensible to propose that the former FAs would be considerably higher in preterm infants fed hindmilk. Current literature suggest that supplementations with DHA using tuna oil to lactating mothers of very preterm infants²³, and not directly to these infants¹⁶, may reduce the risk of BPD and hay fever particularly in boys. As we are measuring the fat contents of the composite and hindmilk, we will be able to explore effects on FA status particularly the levels of LC-PUFAs. This will set the basis for a larger study to address potential effects of hindmilk on brain, retina, and neurodevelopment.

In conclusion, EUGR is common in very preterm infants and is associated with short- and long-term morbidities. EUGR is largely due to nutritional deficits which occur despite standard fortification. This is in part due to large variation in human milk contents between mothers. Because very preterm babies need small volumes it is important to maximize their benefits from the small amount they get. To date, there have been very few studies conducted to evaluate benefits of hindmilk use in preterm infants. These studies were mostly small in size, done in countries where fortification is not used or done in more mature infants.^{14,24,25}

3. Why this is important

This study represents an innovation in optimized nutrient delivery that may have a significant impact on morbidity of very preterm infants. This study would, (i) explore growth benefits of feeding hindmilk to very preterm infants, (ii) provide better understanding of the role of hindmilk in achieving favorable FAs profile (higher DHA and EPA proportions), (iii) will set the basis for a larger study to evaluate effects of hindmilk on BPD, ROP and neurodevelopment and (iv) may lead to a practice change to utilize hindmilk earlier to prevent slow growth velocity and EUGR. In addition, we need to systematically evaluate our current practices of hindmilk use with a prospective and detailed nutrition assessment.

4. How you are going to do it

4.1 Methodology:

Study design: This will be a prospective cohort study in very preterm infants admitted to NICU at Foothills Medical Centre.

Inclusion Criteria:

- Very preterm infants (<32 weeks at birth)
- On full enteral feeds for more than 2 weeks (full feed is defined at the time of reaching 120 ml/kg/day with no parenteral nutrition used)
- Poor weight gain (<15 g/kg per day) despite optimization of energy and protein intakes by RDs (calories intake: 125-135 Kcal/kg per day and protein: 4-4.5 g/kg per day)
- Mothers have enough milk supply (>150% of infant's daily needs)

Exclusion Criteria:

- Congenital anomalies
- Small for gestational age infants (< 10th percentile) at birth

4.2 Study protocol:

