Data on maternal and neonatal characteristics will be collected from their electronic and physical charts. Composite milk, foremilk and hindmilk volumes will be collected from the collection sheet that has been already used in our NICU.

Secondary outcomes EUGR, BPD and ROP will be compared between infants who received hindmilk and the general rates published publically by the Canadian Neonatal Network each year.

4.3 Sample size and feasibility:

Our local data indicate that very preterm infants with extra-uterine growth restriction have an average weight gain of 13 g/kg per day (standard deviation (SD)= 7). A previous small study of 15 preterm infants showed a 7 g (SD= 4.4 g) increase in weight gain when hindmilk was fed.¹⁴ However, our preliminary data indicated a 4 g/kg/day increase in weight gain with hindmilk. The 4 g/kg per day increase is considered clinically significant given it is enough to restore good weight gain (>15g/kg per day) and potentially reduce incidence of EUGR in very preterm infants. Thus, we calculated the sample size based on this difference. In order to permit detection of 4 g/kg per day with 90% power and 0.05 alpha error, a sample of 33 VLBW infants is needed using a calculation of repeated measures in STATA software (STATA 11.0, Texas, USA). Because the cream project included 34 infants in 14 months, we expect to recruit all subjects for the prospective study in 18 months.

4.4 Statistical analysis:

Descriptive statistics using mean, median, SD and interquartile range (IQR) will be used to describe the study population. Paired *t* test will be used to compare average weight gain before and after hindmilk use. Chi-square test will be used to compare EUGR rates and other categorical outcomes. Linear regression analysis will be used to assess the relationships between weight gain and hindmilk and to adjust for potential confounding factors including gestational age and postnatal age. For all tests, a probability of *P* value < 0.05 will be considered statistically significant.

4.5 Definitions:

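### EUGR, BPD, ROP and late-onset sepsis in a selected cohort are tested by unadjusted chi-square against general network rates, so neither a significant nor a null P value can be attributed to hindmilk

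*Combined protocol and SAP*

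**What the plan says.** The study is a single-centre, single-group cohort (Section 4.1). For secondary outcomes 1 to 3 the only comparator is the published rates of the Canadian Neonatal Network. The Note in Section 1 says that these outcomes "will be compared between infants received hindmilk for at least 2 weeks and the rates of these outcomes among NICUs". The third of them is "Incidence of BPD, ROP and late-onset sepsis".

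Section 4.2 restates the comparison: "Secondary outcomes EUGR, BPD and ROP will be compared between infants who received hindmilk and the general rates published publically". This version leaves out late-onset sepsis and the 2-week condition.

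Section 4.4 gives the method: "Chi-square test will be used to compare EUGR rates and other categorical outcomes", and for all tests a P "value < 0.05 will be considered statistically significant". The only adjustment in the plan concerns weight gain: "Linear regression analysis will be used to assess the relationships between weight gain and hindmilk and to adjust for potential confounding factors". Nothing restricts, matches or standardises the network rates, and nothing labels the comparison as descriptive. The limitations in Section 5 cover hindmilk availability and transfusion only.

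**The concern.** A test against an external rate carries information about hindmilk only if the cohort, left untreated, would have had that rate. Section 4.1 makes this implausible, because several entry conditions bear on the outcomes. The key one is "Poor weight gain (<15 g/kg per day) despite optimization of energy and protein intakes by RDs", and the Project Summary says that "EUGR is caused by slow postnatal growth and largely results from energy and protein deficits".

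A significant difference could therefore be produced by case mix alone, and a null result could hide a real effect. This is the only comparison in the plan for EUGR, BPD, ROP and late-onset sepsis, so a reader of the results would have nothing to set against it.

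**Working it through.** **The plan's own figure.** Section 4.3 gives n = 33. Taking the stated SD of 7 as the SD of the change, with a difference of 4, two-sided alpha 0.05 and 90% power: ((1.960 + 1.282) × 7 / 4)² = 32.18, rounded up to 33. The figure reproduces, but it is for the paired weight-gain comparison. No sample size is given for the network comparisons.

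**Direction of the selection, from the documents.**

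- Weight gain below 15 g/kg per day is required (4.1). The Project Summary names slow growth as the cause of EUGR, so this pushes EUGR up. The Project Summary and Section 2 associate EUGR with BPD and ROP, so those rates may differ too.
- SGA infants, below the 10th percentile at birth, are excluded (4.1). EUGR is weight below the 10th percentile (4.5). Removing infants who start below the cut pushes EUGR down.
- Anomalies are excluded, and more than 2 weeks of full feeds, maternal supply above 150% of need and at least 2 weeks of hindmilk are required (4.1 and the Note). These select infants who reached and sustained that feeding status.
- The cohort comes from one centre (4.1) and the reference from a national network.

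For EUGR the first two oppose each other, and the documents give no figures to weigh them. The net bias cannot be signed.

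**Late-onset sepsis and ROP.** The documents state no direct link between slow growth and sepsis. For sepsis the problem is selection on feeding status, together with the lack of a counting window: events before hindmilk start could be counted. The timing point could also apply to ROP.

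**Illustration, EUGR only.** Assumptions:

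- The reference rate is 65%, treated as fixed. This is the Calgary figure at 37 weeks in Section 2, used as a stand-in because the network rate is not in the documents.
- n = 33 and hindmilk has no effect.
- The test is X² = (x − n·p0)² / (n·p0·(1 − p0)) without continuity correction, critical value 3.84.

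Here n·p0 = 33 × 0.65 = 21.45 and n·p0·(1 − p0) = 7.5075.

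- x = 16: 5.45² / 7.5075 = 3.96, significant; x = 17: 4.45² / 7.5075 = 2.64, not.
- x = 27: 5.55² / 7.5075 = 4.10, significant; x = 26: 4.55² / 7.5075 = 2.76, not.

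The test rejects at 16 or fewer, or 27 or more, cases. Exact binomial probabilities of those regions:

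| Cohort EUGR rate from case mix alone | P < 0.05, lower | P < 0.05, higher | Total |
|---|---|---|---|
| 65% (no shift) | 3.8% | 2.8% | 6.6% |
| 75% | 0.1% | 24.7% | 24.8% |
| 80% | 0.0% | 50.0% | 50.0% |
| 50% | 50.0% | 0.0% | 50.0% |

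**Masking.** Suppose selection raises the untreated rate to 80% and hindmilk lowers it to 65%. The first row applies: significant benefit appears in only 3.8% of studies despite a 15-point effect. This case is chosen so that effect and selection cancel.

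**Sensitivity.** With continuity correction (the plan does not say which form is used) the totals are 2.7% with no shift, 13% at 75%, 33% at 80% and 36% at 50%. Since the Note counts only infants with at least 2 weeks of hindmilk, 33 is an upper bound for that group. With 26 to 28 infants the 75% row falls to 14–19% and the 80% row to 32–38%.

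**The case against.** The strongest case against is one of weight. These are secondary outcomes in a small cohort whose stated aim is growth and fatty acids. Items 2 and 3 are worded as incidence, and Section 3 defers effects on BPD and ROP to a larger study. That limits the severity. It does not remove the defect, because Section 4.4 still assigns a test and a threshold. If the comparison is meant only as context, no P value is needed.

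It is also fair that the illustration covers EUGR-type rates only, with assumed shifts. It says nothing numerical about BPD, ROP or sepsis. Even for EUGR, sizing the SGA exclusion would need the SGA share and the proportion of those infants still below the 10th percentile later; neither is in the documents.

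A reader might infer more than the documents support:

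- *That the comparison is biased in favour of hindmilk, or against it.* The selection forces on EUGR oppose each other, so no direction can be claimed.
- *That slow growth ties the cohort to sepsis as it does to EUGR.* No section says so.
- *That sepsis or ROP arising before hindmilk will be counted.* The plan sets no window, so such events could be counted; it does not say that they are.
- *That 25% to 50% is this study's false-positive rate.* Those figures follow from assumed shifts.

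**Conclusion.** The point holds as a design defect and should be corrected. As written, the plan produces P values for EUGR, BPD, ROP and late-onset sepsis that differences between cohort and network can create or hide, and neither a significant nor a null result can be attributed to hindmilk. This rests on the entry criteria and on the absence of any restriction, adjustment or descriptive label, not on the illustrative figures. The grounds are firmest for EUGR, rest on association for BPD and ROP, and for sepsis are limited to feeding-status selection and possible mistiming.

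The actual bias cannot be computed from the documents. The primary paired analysis and secondary outcomes 4 to 6 do not use the network rates and are unaffected.

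**What to change.** In the Section 1 Note and Sections 4.2 and 4.4:

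- Drop the chi-square tests against network rates.
- Report EUGR, BPD, ROP and late-onset sepsis as n/N with exact 95% confidence intervals in the plan's 2-week hindmilk group and, as a check, in all infants who start hindmilk. For example, 20/33 is 61%, with exact interval 42% to 77%.
- Show network rates only as context, with no P value and no causal claim. State the differences beside them: slow gain required, SGA and anomalies excluded, more than 2 weeks of full feeds, maternal supply above 150%, a single centre, and at least 2 weeks of hindmilk.
- Report how many ROP and sepsis events were first diagnosed before and after hindmilk start. Count separately ROP that progresses to treatment and new sepsis episodes after the start. Do not remove infants with earlier diagnoses, or those later events would be lost.
- Use one exposed-group definition and one outcome list in the Note and Section 4.2.

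The cost is mostly wording, plus some chart review to date ROP and sepsis onset. The P values against national rates are given up and these outcomes become descriptive.
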